#### **5.4.4. Vaccination groups**

All safety analyses will be tabulated by vaccination group according to the *as treated* principle. The COVID-19 vaccinations received outside of the study are considered as well. Participants can be present in more than 1 vaccination group as described below. Safety data by vaccination group will be analyzed descriptively.

The following vaccination groups will be presented:

A. Layout 1a:

1. Placebo

All participants who received as first vaccination a placebo injection. All safety data will be reported here until the participant receives an active COVID-19 vaccination (Ad26.COV2.S or outside vaccination).

2. Ad26.COV2.S

All participants who received as first active COVID-19 vaccination Ad26.COV2.S until the participant receives an outside COVID-19 vaccination. This includes participants who initially received placebo and subsequently received Ad26.COV2.S, however only the safety data after the Ad26.COV2.S vaccination until the participant receives an outside

COVID-19 vaccination (if applicable) will be presented here. The safety data of participants who received 2 or more Ad26.COV2.S vaccinations will be presented by post-dose 1, post-dose 2, etc.

**B. Layout 1b:**

**1. mRNA/non-mRNA vaccination + Ad26.COV2.S**

All participants who received as first active COVID-19 vaccination one or more outside mRNA vaccinations or one or more outside non-mRNA vaccinations and subsequently also received an Ad26.COV2.S booster vaccination. Only the safety data after the Ad26.COV2.S vaccination until the participant receives another outside COVID-19 vaccination (if applicable) will be presented here. The safety data of participants who received 2 or more Ad26.COV2.S vaccinations after being primed with non-mRNA/mRNA will be presented by post-dose 1, post-dose 2, etc.

**C. Layout 2:**

**1. Mixed schedule**

The safety data after all other vaccination schedules will be included here. This includes safety data after receipt of only outside vaccinations, after outside vaccinations when primed with Ad26.COV2.S, after outside vaccinations prior to first Ad26.COV2.S vaccination, or any other combination switching between outside vaccinations and Ad26.COV2.S. Note that participants who have a vaccination given outside of the study on the same day as the first study vaccination will have all safety data presented in the mixed schedule vaccination group.

Subjects that switch between Ad26.COV2.S vaccinations and COVID-19 vaccinations given outside of the study (and vice versa) will be presented in the relevant vaccination group depending on the actual vaccination sequence. For example:

**1. Vaccination sequence: Ad26.COV2.S, outside COVID-19 vaccination, Ad26.COV2.S**

Safety data for subjects following this sequence will have data following the first Ad26.COV2.S vaccination up to the date of the outside COVID-19 vaccination presented in the outputs showing first active vaccination is Ad26.COV2.S (layout 1a). All data following the outside COVID-19 vaccination will be presented in the outputs for the mixed schedule vaccination group (layout 2).

**2. Vaccination sequence: outside COVID-19 vaccination, Ad26.COV2.S, outside COVID-19 vaccination**

Safety data for subjects following this sequence will have data following the first outside COVID-19 vaccination up to the date of the Ad26.COV2.S vaccination presented in the outputs for the mixed schedule vaccination group (layout 2). The data following the Ad26.COV2.S vaccination up to the date of the second outside COVID-19 vaccination will be presented in the outputs for Ad26.COV2.S after a COVID-19 vaccination given outside of the study (layout 1b) so long as the previous outside vaccinations were always mRNA or always non-mRNA. The data following the second outside COVID-19 vaccination will be presented in the outputs for the mixed schedule vaccination group (layout 2).

For outputs using layout 1a or 1b, all tables will be produced by study phases and periods per vaccination group, ie post-dose, follow-up D30-M6, follow-up M6-end. For the mixed schedule vaccination group (layout 2) only the AE summary table will be produced presenting data for the entire study period, ie not presented by study phases.

The safety analyses will be performed for the combined double-blind and open-label active phase for the FAS.

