### **1.1. Objectives, Endpoints**

The list of objectives and endpoints for the open-label active surveillance phase and for the open-label passive follow-up phase can be found in PA7. Note that no efficacy evaluations or group comparisons will be performed. All objectives will be evaluated using descriptive statistics.

As of protocol amendment 2, subjects were allowed to receive vaccination outside of the study while still following the same protocol scheduled procedures as those subjects that remained in the study with the Ad26.COV2.S vaccine. The safety for subjects that received other vaccines outside of the study will also be described. No tabulations of efficacy data following vaccines received outside of the study will be provided.

The exploratory endpoints associated with the correlate of risk/efficacy objective will not be evaluated in this study. Correlate of risk/efficacy objectives will be evaluated in the context of study COV3001.

The exploratory endpoints associated with immunogenicity objectives will not be evaluated in the open-label active surveillance phase.

Estimands for the open-label active surveillance analysis:

Objectives	Endpoints/Variable	Population	Intervention	Intercurrent events	Summary measure
Safety	SAEs, AEIs and AESIs from study start until PA7 site approval	Adults>= 18 years old	Ad26.COV2.S, placebo, one or more doses of mRNA + Ad26.COV2.S OR one or more doses of non-mRNA + Ad26.COV2.S, mixed schedule	LTFU	Number of subjects with events and incidence rates per 100 person years per reporting period
Molecularly confirmed a , symptomatic COVID-19 b	Symptomatic COVID-19 according to mild, moderate or severe programmed algorithmic definition, with onset at least 28 days after last vaccination.	Adults>= 18 years old	Single dose Ad26.COV2.S  Two doses Ad26.COV2.S (maximum of 70 days between doses)  Booster dose Ad26.COV2.S (minimum of 71 days between doses)	LTFU-Outside vaccinations	Number of subjects with events and incidence rates per 100 person-years

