[figure not shown]
Objectives	Endpoints/Variable	Population	Intervention	Intercurrent events	Summary measure
Safety	SAEs, AEIs and AESIs from PA7 site approval until end of the study	Adults>= 18 years old	Ad26.COV2.S, placebo, one or more doses of mRNA + Ad26.COV2.S OR one or more doses of non-mRNA + Ad26.COV2.S, mixed schedule	LTFU	Number of subjects with events and incidence rates per 100 person years per reporting period
COVID-19 in terms of (S)AEs, MAAEs, hospitalizations and fatal AEs linked to COVID-19	
 
SAEs and AEs linked to COVID-19
 
MAAEs linked to COVID-19
 
SAEs linked to COVID-19 that require hospitalization
 
Fatal AEs linked to COVID-19
 
	Adults>= 18 years old	Single dose Ad26.COV2.S Two doses Ad26.COV2.S (maximum of 70 days between doses) Booster dose Ad26.COV2.S (minimum of 71 days between doses)	LTFU-Outside vaccinations	Number of subjects with events and incidence rates per 100 person-years
Immunogenicity of Ad26.COV2.S at available timepoints	
 
Analysis of antibodies binding to the SARS-CoV-2 S protein by ELISA
 
Analysis of SARS-CoV-2 neutralizing antibody titers as measured by psVNA and/or wtVNA
 
	Adults>= 18 years old	Two doses Ad26.COV2.S	LTFU- Outside vaccinations	GMR, responder rate  GMR, responder rate
Correlate of immunity	
 
Analysis of binding antibody titer measured by S-ELISA and/or MSD assay, as available for participants having COVID-19 compared to non-infected participants
 
Analysis of SARS-CoV-2 neutralizing antibody titers measured by psVNA or wtVNA,
 
	Adults>= 18 years old	Two doses Ad26.COV2.S	LTFU- Outside vaccinations	Not evaluated in this study.

Objectives	Endpoints/Variable	Population	Intervention	Intercurrent events	Summary measure
	as available for participants having COVID-19 compared to non-infected participants				

LTFU: Lost to follow-up

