#### 5.1.1. Scope of Analysis of the Open-Label Active Follow-up Phase

##### 5.1.1.1. Setting

###### *Unblinding due to availability of other authorized/approved COVID-19 vaccines*

In the double-blind phase of the study, investigators may receive requests to unblind study participants who become eligible to receive other COVID-19 vaccines if/when these are authorized/licensed for use. In these cases, the investigator will discuss with the participant available options and ramifications, including whether they are eligible to receive the Ad26.COV2.S vaccine in the study during the unblinding study visit. If the participant is eligible for a licensed vaccine according to local immunization guidelines or recommendation and if the participant wishes to proceed with the unblinding, the investigator will follow the unblinding procedures. The reason for the unblinding request should be documented. The name and date(s) of administration of the other COVID-19 vaccine should be recorded.

Participants who opt for enrollment in an Expanded Access Program or a Phase 3b study (eg, Sisonke/TOGETHER in South Africa) may be unblinded upon their request and will be encouraged to continue in the VAC31518COV3009 study.

When unblinding, if it is determined that the participant received the Ad26.COV2.S vaccine (and not placebo), the participant will be informed that there are no data on the safety of receiving two different COVID-19 vaccines and no further study vaccination would be permitted in the event he/she chooses to receive the vaccine outside the study. Unblinded participants, whether in the vaccine or control group, will be asked to continue to be followed in this study in line with the schedule of activities. Safety, efficacy, and immunogenicity evaluations will be identical for all participants, including participants that are unblinded to obtain an authorized/licensed COVID-19 vaccine and who remain in the study.

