#### **5.4.6.2. Analysis of Adverse Events**

The number and percentage of participants with at least one particular AE will be tabulated with exact 95% CI, when appropriate. Additionally the incidence rate will also be derived as number of participants with at least one particular AE per 100 person years of follow-up. Unsolicited AEs will be summarized by System Organ Class and Preferred Term.

Denominator for the percentages is the number of participants in the considered population and phase for a certain vaccination group (incidence per 100 participants/phase). Denominator for the incidence rates is the number of person years in the considered population and phase for a certain vaccination group (incidence per 100 person years/phase).

For unsolicited AEs, the following tables will be provided: summary table (including SAEs, SAEs related to study vaccine, MAAEs, MAAEs leading to study discontinuation, MAAEs related to study vaccine, AEs with fatal outcome, AEs related to study vaccine with fatal outcome, AEs related to study vaccine leading to study discontinuation, and AEs leading to study discontinuation), all events, AEs at least grade 3, AEs related to study vaccination, AEs at least grade 3 and related to study vaccination, AEs leading to study discontinuation, SAEs related to study vaccination, SAE (overall, associated with COVID, not associated with COVID), MAAE, selected AEs of interest, fatal AEs, and AESI.

Listings and/or participant narratives will be provided as appropriate, for those participants who die, discontinue study due to an AE, or experience a serious AE.

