#### **5.4.8. Follow-up of Safety data**

Median, minimum, maximum, and interquartile range of the follow-up time from first study vaccination for each of the vaccination groups (except the mixed schedule group) of Section 5.4.4 will be provided for the FAS. Separate tables will be produced for the combined double-blind, open-label active, and open-label passive phase and for the combined double-blind and open-label active phase.

For the tables covering the combined double-blind and open-label active phase:

The follow-up time for an individual who initially received placebo will be censored at i) the date of receipt of Ad26.COV2.S or a vaccination given outside of the study, ii) the date of study discontinuation, iii) the date of study site approval for PA7, or iv) the date of database cutoff, whichever occurred first. The follow-up time for an individual whose first active vaccination was Ad26.COV2.S will be censored at i) the date of receipt of a vaccination given outside of the study, ii) the date of study discontinuation, iii) the date of study site approval for PA7, or iv) the date of database cutoff, whichever occurred first. For the vaccination groups that received first an mRNA or non-mRNA vaccination and then an Ad26.COV2.S vaccination, the follow-up will start from the first Ad26.COV2.S vaccination and will be censored at i) the date of receipt of a vaccination given outside of the study, ii) the date of study discontinuation, iii) the date of study site approval for PA7, or iv) the date of database cutoff, whichever occurred first.

For the tables covering the combined double-blind, open-label active phase, and open-label passive phase the follow-up time is not censored at the date of study site approval of PA7.

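### The SAP assigns AEI and AESI endpoints to the mixed schedule group, but the only table planned for that group lists neither

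*SAP*

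**What the plan says.** **What is promised.** In SAP Section 1.1 the safety endpoint is "SAEs, AEIs and AESIs from study start until PA7 site approval" for the active analysis and "SAEs, AEIs and AESIs from PA7 site approval until end of the study" for the passive analysis. Both estimand rows include the mixed schedule among the interventions. Both give the summary measure as the number of subjects with events and incidence per 100 person-years by reporting period. Section 5.4.1 has AESIs and AEIs collected for every FAS participant throughout the study. Section 5.4.6.1 says they will be tabulated for all FAS and FAS7 participants, with active and passive follow-up kept apart. None of these places makes an exception for the mixed schedule.

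**What is planned for the group.** Section 5.4.4, after the second example sequence, says: "For the mixed schedule vaccination group (layout 2) only the AE summary table will be produced presenting data for the entire study period". It adds that this means no split by study phase.

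**What that table contains.** Section 5.4.6.2 describes it as "summary table (including SAEs, SAEs related to study vaccine, MAAEs, MAAEs leading to study discontinuation, MAAEs related to study vaccine, AEs with fatal outcome", continuing with "AEs related to study vaccine with fatal outcome, AEs related to study vaccine leading to study discontinuation, and AEs leading to study discontinuation". Later in the same sentence, outside the parenthesis, it lists further tables, among them "MAAE, selected AEs of interest, fatal AEs, and AESI".

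**The concern.** The estimand and the general commitment say one thing about this group, and the output restriction says another. A programmer who follows the word 'only' in Section 5.4.4 would produce no AEI or AESI table for the mixed schedule and would find neither among the contents listed for the one table allowed.

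The group matters because it receives all later data from participants who leave the other layouts. Under Sections 5.4.3 and 5.4.4, data following Ad26.COV2.S stop at an outside vaccination, and what follows goes to layout 2. As a hypothetical case, suppose an outside vaccine is given 20 days after Ad26.COV2.S and thrombosis with thrombocytopenia begins on day 25. The event no longer belongs in the layout 1a AESI table, and layout 2 has no AESI table to receive it. The same applies to the Appendix 6 events, such as Guillain-Barré syndrome or myocarditis.

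**Working it through.** The check is a comparison of text. There is no sample size, power or event figure to reproduce.

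**Step 1: endpoints against table contents.** Section 5.4.6.2 lists nine items for the summary table:

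1. SAEs
2. related SAEs
3. MAAEs
4. MAAEs leading to discontinuation
5. related MAAEs
6. fatal AEs
7. related fatal AEs
8. related AEs leading to discontinuation
9. AEs leading to discontinuation

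| Endpoint (Section 1.1) | Row listed in the summary table | Separate table in Section 5.4.6.2 | Separate table allowed for layout 2 (Section 5.4.4) |
|---|---|---|---|
| SAE | Yes | Yes | No |
| AEI | No | Yes | No |
| AESI | No | Yes | No |

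Of 3 endpoints, 1 has a listed row and 3 − 1 = 2 do not. Across the two estimand tables there are 3 × 2 = 6 combinations of endpoint and period, and 2 × 2 = 4 of them have no listed output for this group.

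**Step 2: could another planned output fill the gap?**

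- *The overall summary table in Section 5.4.6.1.* It covers recipients of at least one Ad26.COV2.S dose, so participants with only outside vaccines are left out. It gives numbers and percentages, with no person-year rates, and combines all phases. Its event rows are not specified. It cannot deliver the Section 1.1 estimand for this group.
- *The SAE row of the layout 2 table.* A serious AESI or AEI is counted there but cannot be recognised as one.
- *Listings and narratives in Section 5.4.6.2.* These are for deaths, discontinuations due to an AE, and serious AEs. A non-serious AEI need not appear. Appendix 6 includes peripheral neuropathy and thrombocytopenia, which are not necessarily serious.

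**Step 3: reporting period.** Sections 5.4.5 and 5.4.6.1 require separate active and passive tables, and the Section 5.4.5 example places a participant in the mixed schedule for the passive tables only. Section 5.4.4 speaks of the whole study. Its gloss about study phases may mean only that post-dose and follow-up phases are merged, which would be compatible with one table per period. The text does not settle this.

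**The case against.** The best defence is that the table's contents are introduced as what it includes, so the list may be open. Section 5.4.6.1 promises AESI and AEI tabulation for everyone in the FAS and FAS7, and the overall table's rows are unspecified. On that reading nothing is excluded and a sensible programmer would add the rows. This stands to the extent that one cannot say the events will never be tabulated. It does not remove the conflict: Section 5.4.6.2 names AEIs and AESIs in the same sentence as separate tables, so the natural reading is that they are not summary rows, and Section 5.4.4 withholds separate tables from layout 2.

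A second defence is that the open-label scope was deliberately reduced and is descriptive only. That would justify dropping the endpoints for this group, but Section 1.1 would then have to say so.

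Three stronger readings are tempting and are not supported:

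- *That the SAP says this group has no safety data.* Section 5.1.1.1 records what an unblinded Ad26.COV2.S recipient is told: "there are no data on the safety of receiving two different COVID-19 vaccines". That concerns prior evidence on receiving two vaccines. Nor does it match the group: layout 2 also holds participants with only outside vaccines, and those given solely mRNA or solely non-mRNA vaccines and then Ad26.COV2.S have their subsequent data in layout 1b with the full tables.
- *That pooling biases the group's rate by a known amount.* The SAP openly defines a residual group and claims no estimate of the effect of mixing vaccines. It gives no share of person-time without Ad26.COV2.S, so any dilution figure would only restate an assumption. Splitting the group into columns is a design preference.
- *That the rate denominator is withheld.* Section 5.4.8 gives follow-up time "for each of the vaccination groups (except the mixed schedule group", but this drops only a descriptive summary. Section 5.4.6.2 still sets person-years as the denominator for rates by vaccination group.

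**Conclusion.** The contradiction is real. Sections 1.1 and 5.4.6.1 assign or promise AEI and AESI results for the mixed schedule group. Sections 5.4.4 and 5.4.6.2, read together as written, plan no table and list no row for them. The size is two of three safety endpoints, in both the active and the passive estimand.

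This rests on taking 'only' in Section 5.4.4 literally and on treating the listed contents as the intended rows. It does not show that such events would be lost: serious ones would enter the SAE row and may be covered by listings or narratives. What would be missing is their identification as AEIs or AESIs and their rates per 100 person-years. The SAP should be corrected before the tables are programmed.

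**What to change.** In Section 5.4.4, state that the layout 2 summary table also contains:

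- AESI rows for the three subcategories in Section 5.4.6.1: investigator-identified, selected programmatically, and qualified for assessment;
- AEI rows by the group terms of Appendix 6;
- for each row, the number of participants with events, person-years and the rate per 100 person-years.

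Replace the reference to the entire study period with one table for active follow-up (FAS) and one for passive follow-up (FAS7), each without a split by study phase, so that it agrees with Sections 5.4.5 and 5.4.6.1.

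If the sponsor does not intend to report these endpoints for this group, the minimum is to say so in both Section 1.1 estimand tables and in Section 5.4.6.1.

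The cost is SAP wording and a few rows in one table shell. The events are already collected (Section 5.4.1) and phases are already derived for all vaccinations (Section 5.4.3). The downside is that some rows will be sparse.

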#### **5.4.5. Safety data for the Passive Follow-up Phase**

The safety data collected after PA7 approval encompass SAEs, AEIs, AESIs and MAAEs.

Safety data after the study site approval of PA7 will be presented in separate tables from the active follow-up. All participants of the full analysis set are included who are still active at the time of the study site PA7 approval (FAS7). The same vaccination groups will be presented as in Section 5.4.4 and the same phases as in Section 5.4.2 are used. If subjects received an outside vaccination under PA7 then they are additionally counted in the relevant vaccination group. For example: if a participant received 2 doses of Ad26.COV2.S during the open-label active follow-up and received one additional outside vaccine in the passive follow-up, then they are counted under layout 1a; and not under the mixed schedule group for the active follow-up tables, but they are counted under layout 1a and under the mixed schedule group for the passive follow-up tables.

#### **5.4.6. Adverse Events**

##### **5.4.6.1. Definitions**

SAEs, AESIs, AEIs, and MAAEs leading to study discontinuation, will be tabulated in the outputs covering the active follow-up period (the active follow-up, including the double-blind phase and open-label active phase and separately for the passive follow-up), and MAAEs (including new onset of chronic diseases) will be tabulated in the outputs covering the 6 months after last vaccination period for all participants in the FAS and FAS7 respectively.

An overall summary table for the entire study period (combined double-blind phase, open-label active phase, and open-label passive phase) will also be produced for subjects that received at least 1 dose of Ad26.COV2.S presenting the number and percentage of subjects with events.

The severity of the AEs will be classified as grade 1 to 4 by the investigator.

The AEIs (selected adverse events of interest) are presented by customized group term and MedDRA preferred term as detailed in [Appendix 6 Adverse Events of Interest \(AEI\)](#).

For AESI analyses, the following subcategories are defined:

- Suspected AESIs as identified by the investigator in the database
- Suspected AESIs selected programmatically

Those include all reported AEs that are identified by the selection rule:

- SMQ = “EMBOLIC AND THROMBOTIC EVENTS (SMQ)”  
or
- (SUB\_SMQ1 = “HAEMATOPOIETIC THROMBOCYTOPENIA (SMQ)” and SCOPE in (“BROAD”, “NARROW”)) or HLT (higher level term)=“Thrombocytopenias”
- Qualified for assessment AESIs are thromboembolic events which are reported within 42 days of thrombocytopenia/low platelet counts reported concurrently for the same participant. These events have risk levels assessed by one of the following three criteria:
  - Brighton Collaboration Level (Level 1-5)
  - Center for Disease Control and Prevention (CDC) Tier (non-tier 1/2, tier 1, tier 2)
  - Pharmacovigilance Risk Assessment Committee (PRAC) criteria (confirmed, possible, probable, unlikely, criteria not met)

